Appendix 3.

The SF-36 health survey questionnaire

(The survey was developed by RAND Health on the basis of Medical Outcomes Study; the Russian version was developed and recommended by the Multinational Center for Quality of Life Research)

Name of patient _____

Date of completion _____

Please circle one number for each statement.

1. In general, would you say your health is?

Excellent 1

Very good	2
Good	3
Fair.....	4
Poor	5

2. *Compared to one year ago, how would you rate your health in general now?*

Much better now than one year ago.....	1
Somewhat better now than one year ago	2
About the same	3
Somewhat worse now than one year ago.....	4
Much worse now than one year ago	5

3. The following items are about activities you might do during a typical day. Does your health now limit you in these activities? If so, how much?

	Yes, limited a lot	Yes, limited a little	No, not limited at all
A. Vigorous activities , such as running, lifting heavy objects, participating in strenuous sports.	1	2	3
B. Moderate activities , such as moving a table, pushing a vacuum cleaner, bowling, or playing golf.	1	2	3
C. Lifting or carrying groceries.	1	2	3
D. Climbing several flights of stairs.	1	2	3
E. Climbing one flight of stairs.	1	2	3
F. Bending, kneeling, or stooping.	1	2	3
G. Walking more than a mile .	1	2	3

H. Walking several blocks .	1	2	3
I. Walking one block .	1	2	3
J. Bathing or dressing yourself.	1	2	3

4. During the *past 4 weeks*, have you had any of the following problems with your work or other regular daily activities *as a result of your physical health*:

	Yes	No
A. Cut down the amount of time you spent on work or other activities.	1	2
B. Accomplished less than you would like.	1	2
C. Were limited in the kind of work or other activities.	1	2
D. Had difficulty performing the work or other activities (for example, it took extra effort).	1	2

5. During the *past 4 weeks*, have you had any of the following problems with your work or other regular daily activities *as a result of any emotional problems* (such as feeling depressed or anxious)?

	Yes	No
A. Cut down the amount of time you spent on work or other activities.	1	2
B. Accomplished less than you would like.	1	2
C. Didn't do work or other activities as carefully as usual.	1	2

6. During the *past 4 weeks*, to what extent has your physical health or emotional problems interfered with your normal social activities with family, friends, neighbors, or groups?

Not at all 1

Slightly 2

Moderately 3

Quite a bit 4

Extremely 5

7. How much *bodily* pain have you had during the *past 4 weeks*?

None 1

Very mild 2

Mild 3

Moderate 4

Severe 5

Very severe 6

8. During the *past 4 weeks*, how much did *pain* interfere with your normal work (including both work outside the home and housework)?

Not at all 1

A little bit 2

Moderately 3

Quite a bit 4

Extremely 5

9. These questions are about how you feel and how things have been with you *during the past 4 weeks*. For each question, please give the one answer that comes closest to the way you have been feeling. How much of the time during the *past 4 weeks*...

	All of the time	Most of the time	A good bit of the time	Some of the time	A little of the time	None of the time
A. Did you feel full of pep?	1	2	3	4	5	6
B. Have you been a very nervous person?	1	2	3	4	5	6

C. Have you felt so down in the dumps that nothing could cheer you up?	1	2	3	4	5	6
D. Have you felt calm and peaceful?	1	2	3	4	5	6
E. Did you have a lot of energy?	1	2	3	4	5	6
F. Have you felt downhearted and blue?	1	2	3	4	5	6
G. Did you feel worn out?	1	2	3	4	5	6
H. Have you been a happy person?	1	2	3	4	5	6
I. Did you feel tired?	1	2	3	4	5	6

10. During the *past 4 weeks*, how much of the time has *your physical health or emotional problems* interfered with your social activities (like visiting with friends, relatives, etc.)?

All of the time..... 1
 Most of the time..... 2
 Some of the time..... 3
 A little of the time 4
 None of the time 5

11. How TRUE or FALSE is *each* of the following statements for you?

	Definitely true	Mostly true	Don't know	Mostly false	Definitely false
A. I seem to get sick a little easier than other people	1	2	3	4	5
B. I am as healthy as anybody I know	1	2	3	4	5
C. I expect my health to get worse	1	2	3	4	5
D. My health is excellent	1	2	3	4	5

The survey has the following scales:

1. Physical functioning (PF).
2. Role physical (RP).
3. Bodily pain (BP).
4. General health (GH).
5. Vitality (VT).
6. Social functioning (SF).
7. Role emotional (RE).
8. Mental health (MH).

All the scales of survey constitute two composite measurements: Physical Component Summary (PCS) (scales 1 to 4) and Mental Component Summary (MCS) (scales 5 to 8).

The method for calculating the main parameters of the SF-36 questionnaire

Scale	Questions	Minimal and maximal values	Possible range of values
1. Physical functioning (PF)	3A, 3B, 3C, 3D, 3E, 3F, 3G, 3H, 3I, and 3J	10 – 30	20
2. Role physical (RP)	4A, 4B, 4C, and 4D	3 – 8	4
3. Bodily pain (BP)	7 and 8	2 – 12	10

4. General health (GH)	1, 11A, 11B, 11C, and 11D	5 – 25	20
5. Vitality (VT)	9A, 9E, 9G, and 9I	4 – 24	20
6. Social functioning (SF)	6 and 10	2 – 10	8
7. Role emotional (RE)	5A, 5B, and 5C.	3 - 6	3
8. Mental health (MH)	9B, 9C, 9D, 9F, 9H.	5 – 30	25

For items 6, 9A, 9E, 9D, 9H, 10, and 11, the count-down is applied.

The formula for calculating the values:

$$[(\text{actual value of the scale}) - (\text{minimal possible value on the scale})] : (\text{possible range of values}) \times 100.$$

Requirements for presenting the results:

1. Number of cases per each parameter should be indicated;
2. Descriptive statistics: $M \pm SD$, Me (LQ; UQ), % (n/N);
3. Accuracy of results (estimates, P value); Confidence interval (for main results of the study) and P value;
4. Statistical methods (parametric and non-parametric) and statistical packages should be mentioned.

The recommended statistical packages for the data processing are StatSoft Statistica v.6.0, and SPSS 9.0.

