1.2 Objectives

Primary objective is to describe antihypertensive and hypolipidaemic effectiveness of a triple single-pill combination of amlodipine, atorvastatin and perindopril at 12 weeks in patients with arterial hypertension (HTN) and dyslipidemia in the daily clinical practice.

Secondary objectives

- To determine the proportion of patients who reached systolic (SBP) and diastolic blood pressure (DBP) target goals at weeks 4 and 12 of the observation period respectively.
- To determine the proportion of patients who reached LDL-C target goals at week 12 of the observation period.
- To evaluate the quality of life of patients at visit 1 (V1) and visit 2 (V2) as compared to visit 0 (V0) respectively.
- To evaluate the adherence to treatment with the fixed dose combination (FDC) of amlodipine/atorvastatin/perindopril in patients included into the study at V1 and V2 as compared to V0.
- To evaluate predictors of reaching BP and LDL-C target goals in the study population.

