- Proportion of patients aged 18-64 years at high CV risk who reached SBP <130 and \geq 120 mm Hg and DBP between 70 and79 mm Hg at week 12 of the observation period in the subgroups of patients receiving SPC of amlodipine/atorvastatin/perindopril in the following dosages 5;20;5 mg and 5;20;10 mg and 5;10;5 mg respectively;
- Proportion of patients older than 65 years at high CV risk who reached SBP \leq 139 and \geq 130 mm Hg and DBP between 70 and79 mm Hg at week 12 of the observational period in the subgroups of patients receiving SPC of amlodipine/atorvastatin/perindopril in the following dosages 5;20;5 mg and 5;20;10 mg and 5;10;5 mg respectively;

- Proportion of patients at high CV risk who reached decrease of LDL-C from BL $\geq 50\%$ and reached target $<1,8$ mmol/l (55 mg/dl) at week 12 of the observation period in the subgroups of patients receiving SPC of amlodipine/atorvastatin/perindopril in the following dosages 5;20;5 mg and 5;20;10 mg and 5;10;5 mg respectively;
- Proportion of patients aged 18-64 years at moderate CV risk who reached SBP <130 and ≥ 120 mm Hg and DBP between 70 and 79 mm Hg at week 12 of observational period in the subgroups of patients receiving SPC of amlodipine/atorvastatin/perindopril in the following dosages 5;20;5 mg and 5;20;10 mg and 5;10;5 mg respectively;
- Proportion of patients older than 65 years at moderate CV risk who reached SBP ≤ 139 and ≥ 130 mm Hg and DBP between 70 and 79 mm Hg at week 12 of the observation period in the subgroups of patients receiving SPC of amlodipine/atorvastatin/perindopril in the following dosages 5;20;5 mg and 5;20;10 mg and 5;10;5 mg respectively;
- Proportion of patients at moderate CV risk who reached LDL-C $< 2,6$ mmol/l (100 mg/dl) at week 12 of the observation period in the subgroups of patients receiving SPC of amlodipine/atorvastatin/perindopril in the following dosages 5;20;5 mg and 5;20;10 mg and 5;10;5 mg respectively;
- Mean change from V0 in scores of the SF-36 questionnaire assessed at V1 and V2;
- Proportion of patients with high, moderate and low adherence to the treatment with SPC of amlodipine/atorvastatin/perindopril at V1 as compared to V0 via medication adherence scale;
- Proportion of patients with high, moderate and low adherence to the treatment with SPC of amlodipine/atorvastatin/perindopril at V2 as compared to V0 via medication adherence scale;
- Association between the fact of achieving target BP levels at week 12 and baseline BP and LDL-C levels;

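### The SF-36 scoring key in Appendix 3 cancels out Social Functioning and mis-scores General Health; two other scale ranges do not match the item codes

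*Combined protocol and SAP*

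**What the plan says.** Section 1.2 lists quality of life at V1 and V2, compared with V0, as a secondary objective. Section 1.3 turns it into a variable: "Mean change from V0 in scores of the SF-36 questionnaire assessed at V1 and V2". The scoring method is in Appendix 3. A table gives the items, the minimum and maximum, and the range of each of the eight scales. A formula rescales the raw sum by subtracting the minimum, dividing by the range and multiplying by 100. One sentence says which items are reversed first: "For items 6, 9A, 9E, 9D, 9H, 10, and 11, the count-down is applied".

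Item 9 is listed by letter and item 11 is not. Items 1, 7 and 8 are not listed. The General Health row of the table uses items "1, 11A, 11B, 11C, and 11D". The appendix adds that "All the scales of survey constitute two composite measurements", a physical one (scales 1 to 4) and a mental one (scales 5 to 8), but gives no formula for either. It does not say for any scale whether a higher score means better or worse health.

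**The concern.** Items summed into one scale must point the same way after reversal. The printed response codes suggest that two scales fail this.

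- **Social Functioning.** Item 6 starts at *Not at all* = 1, the best answer. Item 10 ends at "None of the time 5", also the best answer. The key treats both alike.
- **General Health.** Item 1 has *Excellent* = 1 and is not reversed. Item 11 mixes negative statements such as "C. I expect my health to get worse" with positive ones such as "D. My health is excellent" on one true-to-false coding, yet it is listed whole.

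Two table rows (Role Physical and Bodily Pain) also looked inconsistent with the item codes.

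Section 4.1 gives data entry and analysis to a subcontractor, and the documents offer no other key. If this one is followed, a real improvement could be reported as no change or as deterioration, and the output need not show that anything is wrong.

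**Working it through.** **Inputs.** Everything comes from Appendix 3: the printed response codes, the reversal list, the table's minima and ranges, and the formula score = (raw − minimum) / range × 100. An item coded 1 to m is reversed as m + 1 − code.

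**Printed ranges against the codes.** Summing item minima and maxima reproduces six of the eight rows: Physical Functioning 10–30 (range 20), General Health 5–25 (20), Vitality 4–24 (20), Social Functioning 2–10 (8), Role Emotional 3–6 (3), Mental Health 5–30 (25). Two do not reproduce:

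- Role Physical: four items coded 1–2 give 4–8, range 4. Printed: 3–8, range 4.
- Bodily Pain: item 7 (1–6) plus item 8 (1–5) gives 2–11, range 9. Printed: 2–12, range 10.

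**Best and worst respondent under the key as written.**

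| Scale | Best: raw, score | Worst: raw, score |
|---|---|---|
| Social Functioning | 5 + 1 = 6, (6 − 2)/8 = 50 | 1 + 5 = 6, 50 |
| General Health, 11 reversed whole | 1 + 1 + 5 + 1 + 5 = 13, (13 − 5)/20 = 40 | 5 + 5 + 1 + 5 + 1 = 17, 60 |
| General Health, only 11B and 11D reversed | 1 + 5 + 5 + 5 + 5 = 21, 80 | 5 + 1 + 1 + 1 + 1 = 9, 20 |
| Bodily Pain | 1 + 1 = 2, (2 − 2)/10 = 0 | 6 + 5 = 11, 90 |
| Role Physical | 8, (8 − 3)/4 = 125 | 4, 25 |
| Physical Functioning, Vitality, Role Emotional, Mental Health | 100 | 0 |

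(General Health items are in the order 1, 11A, 11B, 11C, 11D; scores are after multiplying by 100.) Vitality and Mental Health come out right, which supports this reading of the reversal rule.

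**Change scores, Social Functioning.** One step on one item is worth 100/8 = 12.5 points. If items 6 and 10 improve by a and b steps, the written key gives 12.5 × (a − b), while a consistent key gives 12.5 × (a + b). Equal improvement of 1, 2, 3 or 4 steps reads 0 each time instead of +25, +50, +75 or +100. With a = 2 and b = 1 it reads +12.5 instead of +37.5. If item 10 improves more than item 6, the sign is wrong. Reversing neither item also gives 50/50; reversing item 6 alone gives 100/0.

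**Change scores, General Health.** One step on one item is worth 100/20 = 5 points. With all five items one step better:

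- Item 11 reversed whole: −5 for each of 1, 11A and 11C, +5 for each of 11B and 11D, total −5.
- Only 11B and 11D reversed: −5 for item 1, +5 for each of the other four, total +15.
- Consistent key: +25.

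A full worst-to-best change reads 40 − 60 = −20, or 80 − 20 = +60, instead of +100.

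**Bodily Pain and Role Physical.** Both pain items run the same way and neither is reversed, so nothing cancels. One step better on both reads −2/10 × 100 = −20: the score falls as pain improves, whereas Physical Functioning, Role Physical, Vitality, Role Emotional and Mental Health rise with better health. In Role Physical, one item better is 1/4 × 100 = +25 with a minimum of either 3 or 4, so the slip shifts levels and cancels in changes.

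**The case against.** The subcontractor may use a standard scoring program and never apply this key; Section 4.2 does not refer to it. That is possible, but the documents do not say so, and this is the only key they contain.

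The wrong sign for General Health depends on reading item 11 as all four statements. That stands as a limit on the claim. The whole-item reading is the more natural one, because item 9 is listed by letter and item 11 is not. The part that holds on either reading is that item 1 works against the other items, so a full worst-to-best change reads +60 at most instead of +100.

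The zero change in Social Functioning holds exactly only when both items move by the same number of steps. This is right. More generally, the score reports the difference between the two item changes where it should report their sum.

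Bodily Pain is internally coherent, and its printed 2–12 and range of 10 agree with each other, so a recode of items 7 and 8 may have been left out. If so, the 0/90 and −20 figures do not apply. This scale therefore needs clarification and is not shown to be mis-scored. Role Physical is probably a typing slip, with no effect on the change variable.

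Finally, Section 4.2 calls the analysis descriptive and exploratory. That limits the consequence but does not make a null or reversed result acceptable for a stated secondary variable.

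**Conclusion.** The concern holds. Followed as written, the key makes Social Functioning unable to separate the best respondent from the worst (50/50), on any reading that treats items 6 and 10 alike. General Health is mis-scored on both readings of item 11: the wrong sign (40/60) if it is reversed whole, or changes cut to 60% (80/20) when all five items move together if only 11B and 11D are reversed. Bodily Pain needs its direction stated and its range reconciled, and Role Physical needs its minimum corrected. Physical Functioning, Vitality, Role Emotional and Mental Health are scored correctly.

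The figures assume that the printed codes are the ones entered, that Appendix 3 is the key used, and, for Bodily Pain, that no unprinted recode was intended. Any effect on the two summary measures cannot be sized, because they have no formula. The blood pressure and LDL-C primary variables are not touched. The point should be fixed before analysis.

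**What to change.** Confirm the key against the instrument's own scoring instructions. The wording below is derived only from consistency with the printed codes. Then:

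1. Replace the reversal sentence with: reverse items 1, 6, 9A, 9D, 9E, 9H, 11B and 11D; do not reverse 10, 11A or 11C. Social Functioning and General Health then both score 100 for the best respondent and 0 for the worst.
2. Set Role Physical to 4–8, range 4, which gives 100/0.
3. For Bodily Pain, either reverse items 7 and 8 so that higher is better, or state that a higher score means more pain. Print the recode that produces 2–12 (range 10), or use 2–11 (range 9) if the printed codes are simply summed. With 2–11, best/worst is 100/0 if the items are reversed and 0/100 if they are not. Reversing while keeping 2–12 gives only 90/0.
4. If the physical and mental summaries are to be reported, give their formula.

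The cost is a corrected appendix table and scoring program, which can be tested on an all-best and an all-worst respondent before real data are scored. No new data are needed, provided that item-level answers are entered from the forms; Section 4.1 describes central entry but does not say whether items or totals are entered.

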Appendix 4. Adverse event / Adverse drug reaction / Special Situation Reporting Form

TARGET Protocol № IC4-05351-070-RUS					
Please send this form immediately by [contact] or by email to [contact], or pass it to the associate of the company.					
Year of birth or Age	Gender	Height	Weight	Patient number	
_____ or _____	M / F	_____	_____	_____	
Observed adverse event:				Date of onset	Until (if recovered)
Serious:  No  Yes, because: (please choose below)  Fatal  Life-threatening  Hospitalisation or prolongation of hospitalisation  Persistent or significant disability or incapacity  Congenital anomaly/birth defect  Medically significant				Outcome:  Recovered  Recovered with sequelae  Recovering  Not recovered  Fatal  Unknown	
General disease(s) / Concomitant disease(s) (please indicate year of first diagnoses):					
Course (please enclose relevant findings e.g. laboratory, hospital reports, histology, etc.):					

Causal relationship with the studied Servier drug:

No Yes Not applicable

If yes, please specify dates of treatment with the studied drug in the table below on the first line:

If no or not applicable, please indicate whether the adverse event /special situation is related to a Servier medicinal product (as mentioned in the following table):

 No  Yes please specify which Servier medicinal product:			
Medication list	Daily dosage / application	Administered	Indication
		-	
		-	
		-	
		-	
		-	
Name: Speciality: Address: Phone:			Date: Signature:

[figure not shown]
Special situations:* situations where no adverse events occurred but information needs to be collected: exposure during pregnancy or breastfeeding, abuse, misuse, medication error, overdose, off label use, occupational exposure, lack of efficacy, suspected transmission of infectious agent via a medicinal product, unintended therapeutic benefit ...

Appendix 5. Score Scale

Name: SCORE scale (Systematic Coronary Risk Evaluate)

Source: http://www.heartscore.org/ru_RU

Purpose: clinical tool for the assessment of the fatal CV event risk in the next 10 years. The scale has been developed for the countries with high CV mortality rate (including Russia) based on the following factors: age, smoking, SBP and total cholesterol levels. Level of HDL-C is not taken into consideration in this scale. It is recommended to use SCORE scale to assess risk in asymptomatic patients older than 40 years, without CVD, diabetes mellitus, chronic kidney disease or familial hypercholesterolemia

Interpretation:

Total CV risk according to SCORE scale:

Less than 1% — low.

1 - 4% — moderate.

5% - 9% — high.

> 10% - very high

Appendix 6. Categories of CV risk and target levels of LDL-C [15]

Risk	Definition	Target level of LDL-C, mmol/l (mg/dl)
Extreme	Combination of ACVD ¹ with DM 2 and/or FH or two cardiovascular complications within 2 year ² in a patient with ACVD regardless of optimal hypolipidemic therapy and/or achieved level of LDL-C \leq 1,4 mmol/l	< 1,4 (55), optimal < 1,0 (40)
Very high	
 - Documented CVD with clinical or based on instrumental findings (history of ACS, stable angina, PCI, CAPG or other interventions on the arteries, 	< 1,4 (55) or decrease from baseline \geq 50%

	
Stroke/TIA, atherosclerosis of peripheral arteries)
 
 – Clinically significant atherosclerotic plaque based on CAG/CT (stenosis \geq 50% in 2 coronary arteries) or duplex scan of carotid arteries (stenosis $>$ 50%) – DM + target organs damage + \geq 3 RF and early start of DM 1 with the duration $>$ 20 years – CKD with eGFR $<$ 30 ml/min/1,73 m² – SCORE risk \geq 10% – FH + CVD or RF 	
High	
Important RF Total cholesterol $>$ 8 mmol/l, and/or LDL-C $>$ 4,9 mmol/l and/or BP \geq 180/110 mm Hg
 
 – FH without RF – DM without target organ damage, DM \geq 10 years or with the RF – Moderate CKD with eGFR 30–59 ml/min/1,73 m² – SCORE risk 5–10% – Hemodynamically non-significant atherosclerosis of non-coronary arteries (stenosis 25–49%) 	$< 1,8$ (70) or decrease from baseline $\geq 50\%$
Moderate	
Young patients (DM 1 – younger than 35 years, DM 2 – younger than 50 years) with the duration of DM $<$ 10 years without target organ damage and RF
 
 – SCORE risk 1–5% 	$< 2,6$ (100)
Low	SCORE risk $<$ 1%	$< 3,0$ (116)

Notes: *LDL-C* – Low-density lipoprotein cholesterol; *DM* – diabetes mellitus; *FH* – familial hypercholesterolemia; *ACVD* – atherosclerotic cardiovascular disease; *CVD* – cardiovascular diseases; *ACS* – acute coronary syndrome; *PCI* – percutaneous coronary intervention; *CAPG* – coronary artery bypass grafting; *TIA* – transient ischaemic attack; *ACB* – атеросклеротическая бляшка; *CAG* – coronary angiography; *CT* – computer tomography; *RF* – risk factor; *eGFR* – glomerular filtration rate; *SCORE* Systematic Coronary Risk Evaluation.

1 *CAD*: *angina* 3-4 *FC*, *non-stable angina*, *history of MI*, *ischaemic stroke*, *PCI*, *CAPG*, *angioplastics of carotid arteries or low extremities arteries*, *carotid endarterectomy*, *ilio-femoral*, *femoral-popliteal bypass grafting*. 2 *Miocardial infarction*, *non-stable angina*, *intermittent*

claudication, transient ischaemic attack/ischaemic stroke. 3 Administration of statins in max tolerated dosage in combination with ezetimibe.

Appendix 7 Target office BP levels depending on age and concomitant diseases [15]

Age	Target office SBP mm Hg					Target office DBP mm Hg
	HTN	+ DM	+ CKD	+ CAD	+ Stroke ^a /TIA	
18 – 64 years	< 130 if tolerated but not <120	< 130 if tolerated but not <120	<140 to 130 if tolerated	< 130 if tolerated but not <120	< 130 if tolerated but not <120	70-79
65-79 years ^a	130-139 if tolerated	130-139 if tolerated	130-139 if tolerated	130-139 if tolerated	130-139 if tolerated	70-79
≥ 80 ^b	130-139 if tolerated	130-139 if tolerated	130-139 if tolerated	130-139 if tolerated	130-139 if tolerated	70-79

a Refers to the patients with the history of stroke and not to the BP measure in acute stroke.

b Target levels can be modified in elderly fragile patients.

